Appendix B: Management Algorithms for Nivolumab and Ipilimumab

These general guidelines constitute guidance to the Investigator and may not be appropriate in all circumstances. Deviation from these guidelines will not be considered a protocol deviation. A general principle of immune adverse events is that differential diagnoses should be diligently evaluated according to standard medical practice. Non-inflammatory etiologies should be considered and appropriately treated.

Corticosteroids are a primary therapy for immuno-oncology drug-related adverse events. The oral equivalent of the recommended IV doses may be considered for ambulatory patients with low-grade toxicity. The lower bioavailability of oral corticosteroids should be taken into account when switching to the equivalent dose of oral corticosteroids.

GI Adverse Event Management Algorithm

Rule out non-inflammatory causes. If non-inflammatory cause is identified, treat accordingly and continue I-O therapy. Opiates/narcotics may mask symptoms of perforation. Infliximab should not be used in cases of perforation or sepsis.

[figure not shown]

Patients on IV steroids may be switched to an equivalent dose of oral corticosteroids (e.g. prednisone) at start of tapering or earlier, once sustained clinical improvement is observed. Lower bioavailability of oral corticosteroids should be taken into account when switching to the equivalent dose of oral corticosteroids.

Updated 05-Jul-2016

Renal Adverse Event Management Algorithm

Rule out non-inflammatory causes. If non-inflammatory cause, treat accordingly and continue I-O therapy

[figure not shown]

Patients on IV steroids may be switched to an equivalent dose of oral corticosteroids (e.g. prednisone) at start of tapering or earlier, once sustained clinical improvement is observed. Lower bioavailability of oral corticosteroids should be taken into account when switching to the equivalent dose of oral corticosteroids.

Updated 05-Jul-2016

Pulmonary Adverse Event Management Algorithm

Rule out non-inflammatory causes. If non-inflammatory cause, treat accordingly and continue I-O therapy. Evaluate with imaging and pulmonary consultation.

[figure not shown]

Patients on IV steroids may be switched to an equivalent dose of oral corticosteroids (e.g. prednisone) at start of tapering or earlier, once sustained clinical improvement is observed. Lower bioavailability of oral corticosteroids should be taken into account when switching to the equivalent dose of oral corticosteroids.

Updated 05-Jul-2016

Hepatic Adverse Event Management Algorithm

Rule out non-inflammatory causes. If non-inflammatory cause, treat accordingly and continue I-O therapy. Consider imaging for obstruction.

Patients on IV steroids may be switched to an equivalent dose of oral corticosteroids (e.g. prednisone) at start of tapering or earlier, once sustained clinical improvement is observed. Lower bioavailability of oral corticosteroids should be taken into account when switching to the equivalent dose of oral corticosteroids.

[figure not shown]
*I-O therapy may be delayed rather than discontinued if AST/ALT \leq 8 x ULN or T.bili \leq 5 x ULN.

**The recommended starting dose for grade 4 hepatitis is 2 mg/kg/day methylprednisolone IV.

Updated 05-Jul-2016

Endocrinopathy Management Algorithm

Rule out non-inflammatory causes. If non-inflammatory cause, treat accordingly and continue I-O therapy. Consider visual field testing, endocrinology consultation, and imaging.

[figure not shown]

Patients on IV steroids may be switched to an equivalent dose of oral corticosteroids (e.g. prednisone) at start of tapering or earlier, once sustained clinical improvement is observed. Lower bioavailability of oral corticosteroids should be taken into account when switching to the equivalent dose of oral corticosteroids.

Updated 05-Jul-2016

Skin Adverse Event Management Algorithm

Rule out non-inflammatory causes. If non-inflammatory cause, treat accordingly and continue I-O therapy.

Patients on IV steroids may be switched to an equivalent dose of oral corticosteroids (e.g. prednisone) at start of tapering or earlier, once sustained clinical improvement is observed. Lower bioavailability of oral corticosteroids should be taken into account when switching to the equivalent dose of oral corticosteroids.

[figure not shown]
*Refer to NCI CTCAE v4 for term-specific grading criteria.

^If SJS/TEN is suspected, withhold I-O therapy and refer patient for specialized care for assessment and treatment. If SJS or TEN is diagnosed, permanently discontinue I-O therapy.

Updated 05-Jul-2016

Neurological Adverse Event Management Algorithm

Rule out non-inflammatory causes. If non-inflammatory cause, treat accordingly and continue I-O therapy.

Patients on IV steroids may be switched to an equivalent dose of oral corticosteroids (e.g. prednisone) at start of tapering or earlier, once sustained clinical improvement is observed. Lower bioavailability of oral corticosteroids should be taken into account when switching to the equivalent dose of oral corticosteroids.

Updated 05-Jul-2016

Appendix C: RECIST 1.1 Criteria

Measurable disease: Measurable lesions are defined as those that can be accurately measured in at least one dimension (longest diameter to be recorded) as >20 mm by chest x-ray, as >10 mm with CT scan, or >10 mm with calipers by clinical exam. All tumor measurements must be recorded in millimeters (or decimal fractions of centimeters).

Note: Tumor lesions that are situated in a previously irradiated area might or might not be considered measurable.

Malignant lymph nodes: To be considered pathologically enlarged and measurable, a lymph node must be >15 mm in short axis when assessed by CT scan (CT scan slice thickness recommended to be no greater than 5 mm). At baseline and in follow-up, only the short axis will be measured and followed.

Non-measurable disease: All other lesions (or sites of disease), including small lesions (longest diameter <10 mm or pathological lymph nodes with ≥ 10 to <15 mm short axis), are considered non-measurable disease. Bone lesions, leptomeningeal disease, ascites, pleural/pericardial effusions, lymphangitis cutis/pulmonitis, inflammatory breast disease, and abdominal masses (not followed by CT or MRI), are considered as non-measurable.

Note: Cystic lesions that meet the criteria for radiographically defined simple cysts should not be considered as malignant lesions (neither measurable nor non-measurable) since they are, by definition, simple cysts.

‘Cystic lesions’ thought to represent cystic metastases can be considered as measurable lesions, if they meet the definition of measurability described above. However, if non-cystic lesions are present in the same patient, these are preferred for selection as target lesions.

Target lesions. All measurable and/or evaluable lesions up to a maximum of 2 lesions per organ and 5 lesions in total, representative of all involved organs, should be identified as **target lesions** and recorded and measured at baseline. Target lesions should be selected on the basis of their size (lesions with the longest diameter), be representative of all involved organs, but in addition should be those that lend themselves to reproducible repeated measurements. It may be the case that, on occasion, the largest lesion does not lend itself to reproducible measurement in which circumstance the next largest lesion which can be measured reproducibly should be selected. A sum of the diameters (longest for non-nodal lesions, short axis for nodal lesions) for all target lesions will be calculated and reported as the baseline sum diameters. If lymph nodes are to be included in the sum, then only the short axis is added into the sum. The baseline sum diameters will be used as reference to further characterize any objective tumor regression in the measurable dimension of the disease.

Non-target lesions. All other lesions (or sites of disease) including any measurable lesions over and above the 5 target lesions should be identified as **non-target lesions** and should also be recorded at baseline. Measurements of these lesions are not required, but the presence, absence, or in rare cases unequivocal progression of each should be noted throughout follow-up.

Methods for Evaluation of Measurable Disease

Clinical lesions: Clinical lesions will only be considered measurable when they are superficial (e.g., skin nodules and palpable lymph nodes) and ≥ 10 mm diameter as assessed using calipers (e.g., skin nodules). In the case of skin lesions, documentation by color photography, including a ruler to estimate the size of the lesion, is recommended.

Conventional CT and MRI: This guideline has defined measurability of lesions on CT scan based on the assumption that CT slice thickness is 5 mm or less. If CT scans have slice thickness greater than 5 mm, the minimum size for a measurable lesion should be twice the slice thickness. MRI is also acceptable.

Response Criteria

Evaluation of Target Lesions (RECIST 1.1)

Complete Response (CR): Disappearance of all target lesions. Any pathological lymph nodes (whether target or non-target) must have reduction in short axis to <10 mm.

Partial Response (PR): At least a 30% decrease in the sum of the diameters of target lesions, taking as reference the baseline sum diameters

Progressive Disease (PD): At least a 20% increase in the sum of the diameters of target lesions, taking as reference the smallest sum on study (this includes the baseline sum if that is the smallest on study). In addition to the relative increase of 20%, the sum must also demonstrate an absolute increase of at least 5 mm. (Note: the appearance of one or more new lesions is also considered progressions).

Stable Disease (SD): Neither sufficient shrinkage to qualify for PR nor sufficient increase to qualify for PD, taking as reference the smallest sum diameters while on study.

Evaluation of Non-Target Lesions

Complete Response (CR): Disappearance of all target lesions. Any pathological lymph nodes (whether target or non-target) must have reduction in short axis to <10 mm.

Partial Response (PR): At least a 30% decrease in the sum of the diameters of target lesions, taking as reference the baseline sum diameters

Progressive Disease (PD): At least a 20% increase in the sum of the diameters of target lesions, taking as reference the smallest sum on study (this includes the baseline sum if that is the smallest on study). In addition to the relative increase of 20%, the sum must also demonstrate an absolute increase of at least 5 mm. (Note: the appearance of one or more new lesions is also considered progressions).

Stable Disease (SD): Neither sufficient shrinkage to qualify for PR nor sufficient increase to qualify for PD, taking as reference the smallest sum diameters while on study.

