4.0 Study Population

4.1 Inclusion Criteria

1. Subjects must have signed and dated an IRB-approved written informed consent form prior to the performance of any protocol-related procedures that are not part of standard care.
2. Colorectal or appendiceal mucinous adenocarcinoma with peritoneal-only metastatic disease. It is recognized that in some patients, peritoneal disease will predominate without distinction of the site of origin, and such patients will be eligible.
3. Microsatellite stable by PCR and/or mismatch repair proficient by immunohistochemistry
4. ECOG performance status of 0 or 1
5. Prior therapy with a fluoropyrimidine, oxaliplatin, and irinotecan unless contraindicated or refused. Prior treatment with antiangiogenic and/or anti-EGFR antibody therapy is permitted but not required
6. Measurable disease by RECIST v. 1.1
7. Laboratory parameters (within 14 days prior to the start of treatment):
 - a. Absolute neutrophil count \geq 1500/ μ L
 - b. Platelets \geq 100,000/ μ L
 - c. Hemoglobin \geq 9.0 g/dL
 - d. PT/INR or PTT \leq 1.5xULN
 - e. Creatinine \leq 1.5xULN OR creatinine clearance \geq 50 mL/min by Cockcroft-Gault formula
 - f. Total bilirubin \leq 1.5xULN
 - i. Subjects with Gilbert's Syndrome must have a total bilirubin level of \leq 3.0xULN
 - g. Albumin \geq 3.0 g/dL
 - h. AST and/or ALT: \leq 3.0xULN
8. Subjects with HIV are permitted provided they meet the following criteria:
 - a. CD4+ cell count \geq 250 cells/mm³
 - b. No history of AIDS-defining conditions other than low CD4+ count
 - c. If subject is on antiretroviral therapy, there must not be expected significant drug-drug interactions with study treatment

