Complete response, partial response, or stable disease	Cannot have met criteria for progression before complete response, partial response, or stable disease	Can have had iUPD (one or more instances), but not iCPD, before CR, PR, or SD
New lesions	Result in progression; recorded but not measured	Results in iUPD but iCPD is only assigned on the basis of this category if at next assessment additional new lesions appear or an increase in size of new lesions is seen (≥ 5 mm for sum of new lesion target or any increase in new lesion non-target); the appearance of new lesions when none have previously been recorded, can also confirm iCPD
Confirmation of progression	Not required (unless equivocal)	Required
Consideration of clinical status	Consideration of clinical status	Clinical stability is considered when deciding whether treatment is continued after iUPD

"i" indicates immune responses assigned using iRECIST. RECIST=Response Evaluation Criteria in Solid Tumours. iUPD=unconfirmed progression. iCPD=confirmed progression. iCR=complete response. iPR=partial response. iSD=stable disease.

Table 2: Assignment of timepoint response using iRECIST

	Timepoint response with no previous iUPD in any category	Timepoint response with previous iUPD in any category
Target lesions: i CR; non-target lesions: iCR; new lesions: no	iCR	iCR
Target lesions: iCR; non-target lesions: non-iCR/non-iUPD; new lesions: no	iPR	iPR
Target lesions: iPR; non-target lesions: non-iCR/non-iUPD; new lesions: no	iPR	iPR
Target lesions: iSD; non-target lesions: non-iCR/non-iUPD; new lesions: no	iSD	iSD
Target lesions: iUPD with no change, or with a decrease from last timepoint; non-target lesions: iUPD with no change, or decrease from last timepoint; new lesions: yes	Not applicable	New lesions confirm iCPD if new lesions were previously identified and they have increased in size (≥ 5 mm in sum of measures for new lesion target or any increase for new lesion non-target) or number; if no change is seen in new lesions (size or number) from last timepoint, assignment remains iUPD
Target lesions: iSD, iPR, iCR; non-target lesions: iUPD; new lesions: no	iUPD	Remains iUPD unless iCPD is confirmed on the basis of a further increase in the size of non-target disease (does not need to meet RECIST 1.1 criteria for unequivocal progression)

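### Appendix C's non-target block repeats the target-lesion rules, so RECIST 1.1 as written neither counts non-target progression as PD nor lets persisting non-nodal non-target disease withhold CR

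*Combined protocol and SAP*

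**What the plan says.** Appendix C first tells the assessor how to record non-target disease: "Measurements of these lesions are not required, but the presence, absence, or in rare cases unequivocal progression of each should be noted throughout follow-up". It then gives response criteria under two headings, one for target lesions and one reading "Evaluation of Non-Target Lesions". The second block opens with "Complete Response (CR): Disappearance of all target lesions" and continues with PR, PD and SD, all expressed through the sum of target diameters. The only non-target element in the CR definition is that pathological nodes must fall below 10 mm in short axis. The only progression trigger outside the target sum is a note that new lesions count.

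Section 9.1.2.1 (PFS) and Section 9.1.2.3 (response rate) point to Appendix C for RECIST 1.1. Section 9.2 commits to response rate, PFS and duration of response by both RECIST 1.1 and iRECIST, with 90% confidence intervals. Section 9.1.1 scores the primary endpoint by iRECIST in Appendix D.

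Appendix D, Table 2 does use non-target status. One row, "Target lesions: iSD, iPR, iCR; non-target lesions: iUPD; new lesions: no", is assigned iUPD when there is no previous iUPD. The same row says that a later confirming increase "does not need to meet RECIST 1.1 criteria for unequivocal progression", which presupposes that such criteria are written down somewhere.

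**The concern.** A definition that scores non-target disease by the target sum is not a non-target definition. It leaves two gaps in the RECIST 1.1 rules. Recorded unequivocal progression of existing non-target lesions leads to no response category. Recorded persistence of non-nodal non-target disease does not stop a CR. Appendix C also has no rule that combines target, non-target and new-lesion findings into one overall response.

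Non-target disease is likely to be common in this trial. Section 4.1 enrols "Colorectal or appendiceal mucinous adenocarcinoma with peritoneal-only metastatic disease". Appendix C classes "Bone lesions, leptomeningeal disease, ascites, pleural/pericardial effusions" and similar findings as non-measurable, and limits target lesions to "up to a maximum of 2 lesions per organ and 5 lesions in total". What is at stake is whether the RECIST 1.1 secondary results can be reproduced from the written definition, and whether they can be compared with the iRECIST results reported beside them.

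**Working it through.** The plan states no figure on this point, so the check is mainly a comparison of texts.

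**1. The two blocks.** Setting CR, PR, PD and SD under the target heading against the same four under the non-target heading, 4 of 4 are identical.

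**2. Can the copied text work for non-target lesions?** No. It needs a sum of diameters of target lesions, while Appendix C does not require non-target lesions to be measured.

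**3. Is the rule written elsewhere?** Appendix C contains only the recording instruction. Table 2 of Appendix D assigns iRECIST categories and takes its lesion definitions from RECIST 1.1. The reference list in Section 16.0 has an iRECIST source but no RECIST 1.1 source.

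**4. Two patients scored both ways, neither with new lesions or an earlier iUPD.**

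| Findings | Appendix C as written | Appendix D, Table 2 |
|---|---|---|
| Target sum stable; existing non-target disease unequivocally worse | SD | iUPD |
| Target lesions gone; non-nodal non-target disease (such as ascites) persists, not progressing | CR | iPR |

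Because the two Appendix C blocks are identical, both return the same category for each patient. No way of combining them can give a different answer. The first row conflicts with the text of Appendix D, which treats an initial iUPD as progression by RECIST 1.1. The second conflicts with the Table 2 footnote, which says the CR, PR and SD categories agree when there is no pseudoprogression.

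**5. Which endpoints move.**
- RECIST 1.1 PFS and duration of response: the progression date is late or missing.
- CR/PR split and duration of CR (Section 9.1.2.4): a PR can be recorded as a CR. Response rate is unchanged by this.
- Response rate: affected only if a target response coexists with or follows the uncounted progression, because Table 1 of Appendix D bars a RECIST 1.1 response after progression. With 21 evaluable subjects, one such patient is 1/21 = 4.8 percentage points.
- Primary six-month PFS: unchanged in both cases, because Table 2 supplies the category.

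**6. Size per missed event.** The progression date moves to the next assessment at the earliest, unless death comes first. At 30.44 days per month:
- scheduled 8 weeks: 56/30.44 = 1.84 months;
- 12 weeks, the upper end that Section 5.0 allows after week 24: 84/30.44 = 2.76 months;
- confirmatory scan at 4 to 8 weeks: 28/30.44 = 0.92 to 1.84 months.

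Scheduled scans also carry a window of ±2 weeks. If no later Appendix C event or death is recorded, Section 9.1.2.1 makes the patient a censored observation. For scale, Section 9.2 quotes a historical median PFS of about 2 months, so one interval is a large shift for an individual patient. It is not an estimate of the shift in the median.

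**7. How much disease is non-target.** The documents do not say whether the peritoneum counts as one organ. If it does, at most 2 peritoneal lesions can be targets; if not, at most 5. All remaining lesions and any ascites are non-target.

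**The case against.** The strongest reply is that the intended rule can be assembled from the documents. Appendix D equates initial iUPD with RECIST 1.1 progression, Table 2 gives iUPD for non-target progression, and the footnote aligns the remaining categories. An experienced assessor would probably score both patients as intended. That stands as a reason to expect sensible practice. It does not supply the definition: Table 2 takes non-target status as an input and refers back to RECIST 1.1 for it, and the only RECIST 1.1 response rules provided define that status by target lesions. The inference is circular.

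A second reply is that, without a combining rule, the overall Appendix C result is undefined and not SD or CR. It is true that no combining rule exists. But the two identical blocks agree for each patient, and nothing in Appendix C points to another category.

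A third reply concerns size, and most of it stands. Appendix C itself calls unequivocal non-target progression rare, and common non-target disease does not make progression confined to it common. The 12-week interval appears only in Section 5.0; Sections 3.0 and 7.2.2 say every 8 weeks. Appendix D also says every 8 weeks, yet its example visits (day 1 of cycles 3 and 5) are 2 × 56 days = 16 weeks apart. After the end-of-study visit, scans follow clinical care (Section 17.0). It is also awkward to censor a patient as progression-free on a scan that records worsening, although the literal rule leads there. Finally, the exposed endpoints are secondary estimates without a hypothesis test.

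**Conclusion.** The concern holds. The RECIST 1.1 response definition that the plan names contains a wrong block, most likely a copying error, and applied literally it contradicts Appendix D in two identifiable situations. The effect is confined to secondary RECIST 1.1 results: PFS, duration of response, the CR/PR split and duration of CR, and response rate only in the sequence described. The primary endpoint, sample size and power are unaffected.

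The total effect cannot be calculated because no rate of non-target-only progression is given. Per event, the delay is at least to the next assessment, nominally 0.9 to 2.8 months across the stated schedules, or the event is lost to censoring. This assumes that Appendix C is applied as written, that the stated schedules are followed, and that death does not come first. The block should be corrected before the RECIST 1.1 results are derived.

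**What to change.** Replace the duplicated block in Appendix C with non-target categories that match the recording instruction and Table 2:
- **CR:** all non-target lesions have disappeared, with nodes below 10 mm in short axis.
- **Non-CR/non-PD:** one or more non-target lesions persist without unequivocal progression.
- **PD:** unequivocal progression of existing non-target lesions.

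Add an overall-response rule. Overall RECIST 1.1 CR requires non-target CR; non-target PD or any new lesion gives overall PD, which enters Appendix D as iUPD. Table 2's reference to a RECIST 1.1 criterion for unequivocal progression then has something to point to.

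The cost is a text correction to one appendix. No new assessments are needed, because Appendix C already requires the status of each non-target lesion to be noted throughout follow-up.
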